#### *Secondary Objective*

1. To determine if the change in surface temperature over the course of treatment for cellulitis is predictive of clinical response to therapy. A demonstrated association would allow clinicians to objectively assess treatment progress at the bedside as well as provide a good surrogate outcome in clinical trials. We hypothesize that the temperature

differential will decrease over the course of treatment and predict clinical improvement.

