## Innovation

If positive, our findings would have significant implications for both clinical practice and research. The practicality of the laser thermometer as a bedside diagnostic aid would reduce cellulitis misdiagnoses, improve patient outcomes, and optimize clinical resource use. Moreover, current Food and Drug Administration (FDA) guidelines specify that the primary efficacy endpoint of skin infection trials must be a precisely measured relative decrease in surface area of a lesion [10]. This is a cumbersome approach with minimal clinical utility and significant interobserver differences in measurement. If our results demonstrate that change in surface temperature predicts clinical response, this may become an alternative and more practical outcome measure for response to therapy which is robustly reproducible.

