### *Study Protocol*

Our research team will be notified of eligible patients by direct page or e-mail from the infectious diseases service when a new consultation for cellulitis is requested. Within 6 hours of this notification (and ideally as soon as possible), we will obtain informed consent and enrol the patient. After obtaining informed consent, we will use a non-contact infrared thermometer to measure surface temperature at the site of suspected infection as well other locations on the ipsilateral and contralateral limb. Specifically, in the upper extremities, the surface temperature of the hand (mid point of dorsum) forearm (halfway point at the dorsal surface), and upper arm (approximately 10 cm below acromion process, middle of lateral portion of arm) will be measured in both limbs regardless of site of suspected infection. In the lower extremities, the surface temperature of the foot (mid point on dorsum of foot), shin (middle of leg, approximately 10 cm below tibial tuberosity), and distal thighs (approx. 10cm above superior edge of knee,

middle of thigh) will be consistently recorded. All measurements will be made in triplicate for the first ten patients and if there is very high reproducibility of the measurements in those ten single measurements from then on. If there is moderate to high reproducibility of the measurements we will reduce to duplicate.

Relevant laboratory and clinical information will also be extracted from the chart. Clinical information will include age, sex, medical co-morbidities, medications and clinical measurements (such as vital signs). Biochemical data will include white blood cell count and C-Reactive Protein levels (when available). Microbiological data, including cultures of blood and purulent exudate, will also be considered when available. Treatment data on which antibiotics and duration of therapy will be obtained but only after all initial measurements have been taken to avoid any potential bias in measurement. Treatment data will include the name of the ID physician (all ID physicians will agree via the Divisional Chair) so that appropriate statistical testing can be done to account for differences in the “gold standard” between doctors.

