This data will be collected and managed using either the REDCap electronic data capture tools hosted at the McGill University Health Centre or another secure database system requiring password protected individually identified user accounts to access it [11]. Data will initially be stored by MRN (without name) but after all follow up visits are complete will be coded to ensure patient confidentiality (one-way hash of the MRN). The infectious diseases clinicians will be blinded to the result of the surface temperature measurement.

We will then compare the temperature difference between the affected and non-affected limbs with the current gold standard: the clinical diagnosis of the attending infectious diseases physician. This will yield estimates of sensitivity and specificity of the diagnostic test using expert clinical judgement as the gold standard.

In patients with cellulitis who are admitted for intravenous antibiotic therapy, we will perform daily measurements as described above throughout their admission. We will continue to record clinical data and laboratory data as above throughout admission for these patients. We will ultimately use statistical methods to characterize the relationship between skin surface temperature, expert clinical diagnosis of cellulitis and response to therapy (length of stay, duration of therapy, need for escalation in therapy, etc).

The study will be conducted until enrolment is completed. The anticipated study dates are September 1st 2018 to January 1st 2019.

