### *Statistical Analysis:*

For our primary aim, classical 2 x 2 tables will be used to evaluate the sensitivity and specificity of skin surface temperature in predicting cellulitis, as diagnosed by the attending infectious diseases specialist. A temperature difference of 0.5°C between the area of suspected cellulitis and an average of non-affected areas will be considered significant in the first attempt.

With regards to our secondary aim, we will use multivariate analysis and logistic regression to determine relationships between change in temperature differential and clinical response. Response to therapy will be defined on the basis of clinical and laboratory data and will consider the following information:

- Days of fever (i.e the number of calendar days since enrolment in which a temperature of 38.0 or higher was recorded)
- Days of intravenous antimicrobial therapy for cellulitis
- Days of hospitalization for cellulitis (including days in the ER)
- Total number of days of antibiotics given for cellulitis
- Days to normalization of white blood cell count
- Days to normalization of C-Reactive Protein
- Patient reported outcomes:
  - Patient global impression of improvement scale
    - Select the option which best describes your cellulitis now, as compared to how it was when you arrived in the emergency department:
    - Very much better (1)
    - Much better (2)
    - A little better (3)
    - No change (4)
    - A little worse (5)
    - Much worse (6)
    - Very much worse (7)

*Study Funding and Compensation*

This study is not externally funded. The fees for purchasing the infrared thermometer will be borne by the investigators. Physicians and patients will not receive compensation for their participation in this pragmatic study.

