Our goal was to detect a 12% difference in skin surface temperature between limbs with a statistical power of 80%. Assuming an alpha value of 5%, we estimated that we would need to enroll a minimum of 31 patients. To more confidently establish sensitivity and specificity estimates and to be more certain of an adequate sample size, we sought to enrol 50 patients.

With the “*cutpt*” command in STATA v. 16 (Statacorp LP, USA), we will use Youden’s method² to determine the temperature difference which best differentiated cellulitis from pseudocellulitis. We will then use bootstrapping (500 repetitions) to estimate 95% confidence intervals for the sensitivity, specificity and the area under the receiver operating curve (c-statistic). Then, using the point estimates for sensitivity and specificity we will construct a plot of pre-test vs. post-test probability as a function of test result. We will also calculate the temperature difference which gave the maximal specificity and include it for reference.

Analysis of Improvement of Cellulitis:

For those who were admitted to hospital and who agreed to be followed we will calculate the FDA criteria for early response (percent reduction in the lesion size at 48 to 72 hours compared to baseline) wherein clinical response in a patient generally is defined as a percent reduction in lesion size greater than or equal to 20 percent compared to baseline. With the “*cutpt*” command in STATA v. 16 (Statacorp LP, USA), we will use Youden’s method² to determine the temperature difference which best matches early response. We will then use bootstrapping (500 repetitions) to estimate 95% confidence intervals for the sensitivity, specificity and the area under the receiver operating curve (c-

statistic). We will also calculate the temperature differences which give the maximal sensitivity and specificity and include it for reference.

We will also explore the relationship between change in lesion size and temperature difference between limbs graphically and calculate an estimate of the correlation using the most appropriate regression method based on inspection.

REFERENCES

2. Youden WJ. Index for rating diagnostic tests. *Cancer.* 1950;3(1):32–35.

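### The SAP judges improvement only against lesion size and analyses none of the Protocol's seven response measures, so the secondary objective, with response as the Protocol defines it, has no analysis

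*SAP*

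**What the plan says.** **Protocol.** The Secondary Objective is "To determine if the change in surface temperature over the course of treatment for cellulitis is predictive of clinical response to therapy". A demonstrated association is also meant to "provide a good surrogate outcome in clinical trials". The Statistical Analysis section says: "Response to therapy will be defined on the basis of clinical and laboratory data and will consider the following information". Seven measures follow: days of fever, days of intravenous therapy, days in hospital, total antibiotic days, days to normal white cell count, days to normal CRP, and a seven-point patient global impression of improvement. The predictor is the change in temperature differential, and the stated methods are logistic regression and multivariate analysis.

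The Innovation section says of the lesion-area endpoint in FDA guidance: "This is a cumbersome approach with minimal clinical utility and significant interobserver differences in measurement". It adds that if temperature change predicts response, "this may become an alternative and more practical outcome measure for response to therapy which is robustly reproducible". For admitted patients with cellulitis, the Study Protocol section says "we will perform daily measurements as described above throughout their admission". The measurements described before that point are skin temperatures.

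**SAP.** The Analysis of Improvement section applies to admitted patients who agreed to follow-up. Its response definition is that "clinical response in a patient generally is defined as a percent reduction in lesion size greater than or equal to 20 percent compared to baseline", at 48 to 72 hours. It plans a Youden cut-point for temperature difference against that criterion, with bootstrapped intervals for sensitivity, specificity and the c-statistic. It also plans a graph and a correlation of change in lesion size with temperature difference.

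**The concern.** The two documents answer different questions under the same objective. The Protocol asks whether falling temperature goes with fewer days of fever, treatment and hospital stay, normalising blood tests, and a patient who feels better. The SAP asks whether temperature agrees with lesion size. No text links the two or explains the change.

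The reference standard chosen is also the one the Protocol criticises, and its measurement is not described. A report that follows the SAP could state that temperature predicts clinical response without having analysed any of the Protocol's response measures, including the only patient-reported one. Readers could then take the unexplained move from seven measures to one as a change of outcome.

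**Working it through.** The point is textual, so the main check sets the two documents side by side.

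| Measure | Protocol response list | Protocol data collection (Study Protocol section) | SAP improvement analysis |
|---|---|---|---|
| Days of fever | yes | covered by vital signs | none |
| Days of IV therapy | yes | covered by antibiotic and duration data | none |
| Days in hospital | yes | length of stay named as a response | none |
| Total antibiotic days | yes | covered by antibiotic and duration data | none |
| Days to normal white cell count | yes | named | none |
| Days to normal CRP | yes | named, when available | none |
| Patient global impression | yes | not named, no assessment time | none |
| Lesion size | no | not named | sole reference |

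**Count.** The SAP analyses 0 of the 7 Protocol measures. Its 1 reference measure appears in neither the Protocol's data-collection text nor its response list.

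**Predictor.** The Protocol specifies the change in temperature differential. The SAP refers only to temperature difference and gives no time point, so it is unclear whether the cut-point applies to a baseline value, a value at 48 to 72 hours, or a change.

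**Measurement.** The SAP describes thermometer technique in detail (device, distance, duplicate readings, uncovering the area). Neither document says how lesion size is measured, by whom, or whether that person is blinded to temperature.

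**Stated design figure.** The minimum of 31 patients is based on a 12% between-limb temperature difference. It cannot be reproduced because no standard deviation is given. Nothing here depends on it.

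**Illustration of why the reference matters.** All inputs are assumed; none comes from the documents. Let π be the proportion responding, a the sensitivity and specificity of lesion size for response, and s the sensitivity and specificity of temperature for response, with independent errors.

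- Apparent sensitivity = [πas + (1−π)(1−a)(1−s)] / [πa + (1−π)(1−a)]
- Apparent specificity = [(1−π)as + π(1−a)(1−s)] / [(1−π)a + π(1−a)]

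Worked case with s = 0.80, a = 0.90, π = 0.70:

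- Sensitivity = (0.504 + 0.006)/0.66 = 0.773
- Specificity = (0.216 + 0.014)/0.34 = 0.676

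Apparent sensitivity/specificity across a range, with s = 0.80:

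| a | π = 0.50 | π = 0.70 | π = 0.85 |
|---|---|---|---|
| 0.9 | 0.740/0.740 | 0.773/0.676 | 0.788/0.568 |
| 0.8 | 0.680/0.680 | 0.742/0.579 | 0.775/0.448 |
| 0.7 | 0.620/0.620 | 0.707/0.500 | 0.758/0.375 |

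Accuracy against lesion size therefore need not equal accuracy against clinical response. Under these assumptions it is lower.

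**The case against.** **The SAP does test a form of the objective.** A reader might infer that the secondary objective goes wholly untested. The documents do not support that. The SAP uses a criterion it labels clinical response, and the Protocol's own account is that FDA guidance makes lesion area the primary endpoint of skin infection trials. Comparing a proposed surrogate with that endpoint bears on the surrogate purpose. This stands, and it is why the point is limited to response as the Protocol defines it.

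**The SAP is not confined to the 20% threshold.** The exploratory correlation uses change in lesion size without a cut-off. This also stands, although the reference is still lesion size.

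**A single fixed-time criterion is defensible.** The Protocol gives no rule for combining its seven measures into responder status, and treatment and hospital days partly reflect treatment decisions. Calling an endpoint impractical does not rule it out as a comparator. This is a fair reason to keep the lesion-size analysis. It does not explain why the SAP leaves out the other measures without comment.

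**Availability of data.** It is tempting to say that the Protocol's measures were collected and left unused, or that lesion size was never collected. Neither is established. The seven measures were planned, CRP depended on availability, and the patient scale has no schedule. The Protocol's lists are open-ended, and the SAP's calculation presupposes lesion-size data.

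**The illustration is not evidence about this trial.** That is correct. Its inputs are assumed, and any imperfect reference, including the Protocol's own measures, would produce similar attenuation.

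**Conclusion.** The point holds and should be corrected. The SAP analyses 0 of the Protocol's 7 response measures, omits the planned regression on change in temperature differential, and relies on one reference that the Protocol does not name for collection and does criticise. It gives no reason. The secondary objective as the Protocol defines it therefore has no analysis, and the SAP's result can support only a statement about agreement with lesion size.

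This conclusion rests on the text of the two documents and on no numerical assumption. The attenuation figures show a mechanism and do not estimate its size here. The documents do not show that the change was made with knowledge of results, or that the lesion-size analysis is invalid. The primary diagnostic analysis is not affected.

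**What to change.** 1. In the SAP's improvement section, add the analyses the Protocol planned: relate the change in temperature differential to the patient global impression and to each clinical and laboratory measure available. Rank these measures or label them supportive, and state the time points and how many patients have data for each.
2. Keep the lesion-size analyses, described as agreement with the FDA early-response endpoint. State why they were added, how lesion size was measured, by whom, and whether that person was blinded to temperature. Define the temperature variable and its time point.
3. Limit any statement that temperature predicts clinical response to the measures actually analysed.

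**Cost.** SAP wording and a few further analyses of data the Protocol already planned. There will be several response measures instead of one, hence the ranking or labelling, and some, such as CRP, may be incomplete. The SAP is dated March 2020 and describes recruitment in the past tense, so adding a lesion measurement to the daily schedule may come too late. Documenting what was actually done is the realistic step.

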### *Sample Size*

In order to detect a 12% difference in skin surface temperature between limbs with a statistical power of 80%, assuming an alpha value of 5%, we anticipate that we will need to enrol 31 patients at a minimum. To be certain that we will establish reasonable sensitivity and specificity estimates and that our sample size will be sufficient, we will aim to enrol 50 patients with a diagnosis of cellulitis.

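### The early-response cut-off is chosen and judged in the same small subset without optimism correction, so its sensitivity and specificity will look too good, most of all if non-responders are few

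*SAP*

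**What the plan says.** The SAP section on improvement of cellulitis defines the analysis set as "For those who were admitted to hospital and who agreed to be followed". Overall enrolment is small: the SAP says "we sought to enrol 50 patients", and the protocol's Sample Size section says "we will aim to enrol 50 patients with a diagnosis of cellulitis". Response at 48 to 72 hours is "defined as a percent reduction in lesion size greater than or equal to 20 percent compared to baseline".

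Within that set the SAP will "determine the temperature difference which best matches early response" by Youden's method. It continues: "We will then use bootstrapping (500 repetitions) to estimate 95% confidence intervals for the sensitivity, specificity and the area under" the ROC curve. Two more cut-offs come from the same patients: "We will also calculate the temperature differences which give the maximal sensitivity and specificity and include it for reference".

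A graphical and regression analysis of lesion-size change against the between-limb temperature difference is also planned, with the regression method to be picked after looking at the data.

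For this analysis the SAP does not state:
- the expected number followed or the expected response rate;
- a minimum number of non-responders;
- whether resampling is stratified by response, or what happens to a resample holding only one class;
- whether the cut-off is re-selected in each resample;
- any optimism correction or validation.

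**The concern.** Youden's method searches all cut-offs and keeps the one with the largest sensitivity + specificity − 1. If the same patients then supply the reported sensitivity and specificity, chance separation is counted as performance. The fewer patients in the smaller class, the more room chance has. Here the set is a subset of a study of about 50, split again by response, and non-responders may be the smaller class.

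The use of the result matters. The protocol's secondary objective hopes for a surrogate outcome for trials, and its Innovation section suggests that temperature change might replace measured lesion size as an endpoint. A cut-off whose accuracy is partly an artefact of selection would be weak support for that, and the planned output would not show how much is artefact.

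**Working it through.** **The plan's own figure.** The only sample-size calculation is the minimum of 31 for a 12% temperature difference between limbs (80% power, 5% alpha). No SD is given, so it cannot be reproduced. For a paired two-sided test, 31 patients correspond to a standardised difference of (1.960 + 0.842)/√31 = 0.503, that is, an SD of 12/0.503 ≈ 23.8 percentage points. The calculation concerns limb temperature and does not address the early-response analysis.

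**Inputs.** From the documents: about 50 enrolled, 500 repetitions, a binary split at 20%. Assumed, because the documents do not say: n followed patients (10 to 50, with 30 as the main case) and m non-responders.

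**Step 1: optimism when temperature is pure noise.** Temperature is simulated independently of response, with the direction fixed in advance. The true Youden index J is 0 at every cut-off, so any positive mean is optimism.

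| n | m | mean in-sample J | 95th percentile |
|---|---|---|---|
| 20 | 3 | 0.33 | – |
| 30 | 3 | 0.32 | 0.67 |
| 30 | 6 | 0.25 | 0.50 |
| 30 | 10 | 0.21 | 0.45 |
| 50 | 3 | 0.33 | – |
| 50 | 10 | 0.20 | – |

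At n = 30, m = 3 the mean sensitivity is 0.54 and the mean specificity 0.78 (0.54 + 0.78 − 1 = 0.32). A sanity check is m = 1. The best cut-off then sits at the single non-responder, specificity is 100%, and sensitivity is the share of responders beyond that patient, which averages about one half. The simulation gave 0.49 at n = 30. Over all the settings simulated (n from 10 to 50), mean J ran from 0.18 to 0.50.

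**Step 2: the intervals under the same noise** (300 data sets × 500 unstratified resamples at n = 30; simulation error about 3 points).

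| | m = 3 | m = 10 |
|---|---|---|
| Specificity 100% with interval 100% to 100% | 57% | 13% |
| Interval for J wholly above 0, cut-off held fixed | 46% | 19% |
| Interval for J wholly above 0, cut-off re-selected | 73% | 62% |
| c-statistic interval excludes 0.5 (nominal 5%) | 12% | 6% |

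The mean c-statistic stays at 0.50. The SAP does not plan an interval for J; it is used here to summarise sensitivity and specificity together. Re-selecting the cut-off and taking plain percentiles does not cure the optimism. Re-selection helps only as part of an optimism correction.

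**Step 3: one-class resamples.** If resampling is unstratified, P(no non-responder) = (1 − m/n)^n.
- m = 3, n = 30: 0.9^30 = 0.042, about 21 of 500.
- m = 4, n = 30: (26/30)^30 = 0.014, about 7 of 500.
- m = 6, n = 30: 0.8^30 = 0.0012, about 0.6 of 500.
- m = 10, n = 30: effectively none.

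**Step 4: is a small class plausible?** With a 10% non-response rate, P(3 or fewer non-responders) is 87% at n = 20, 65% at n = 30 and 25% at n = 50. With 30% it is 11%, 1% and about 0.

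**Step 5: would stratifying by response help?** It removes one-class resamples by construction. It leaves the selected cut-off, and so the mean J of 0.32 at n = 30, m = 3, unchanged. In a null simulation at that setting, c-statistic intervals were narrower when stratified and covered 82%, against 86% unstratified. That gap is small, and I read it only as no improvement.

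**The case against.** The strongest reply is that the small class is assumed: nothing in the documents gives the number followed or the response rate. At 30% non-response a class of 3 or fewer is unlikely once 30 are followed. This stands, and it confines the one-class problem to a conditional note. Even at 3 of 30, about 479 of the 500 resamples contain both classes.

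Second, a reader might infer that the SAP specifies a simple, unstratified bootstrap which will break down. The SAP says only that it will bootstrap 500 times. The supportable criticism is that the resampling scheme is unspecified.

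Third, the c-statistic is already planned and is not inflated on average if its direction is fixed. This also stands, and is why it should lead. It is not a complete safeguard: with 3 non-responders its interval is too narrow, and sensitivity and specificity would still be printed uncorrected beside it.

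Fourth, this is a secondary aim in an unfunded pragmatic cohort, and in-sample optimism also affects the diagnostic analysis, which uses the same method. That limits the weight of the point. It does not remove it, because here the patients are fewer and the intended use is a surrogate endpoint.

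The continuous analysis is not a ready-made alternative either. Its method is to be chosen on inspection. It uses the between-limb difference, whereas the protocol's secondary objective concerns change in temperature during treatment.

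**Conclusion.** The point holds for the optimism. As planned, the early-response sensitivity and specificity are jointly biased upward. For a useless marker in 30 followed patients the mean excess in J is about 0.32, 0.25 and 0.21 with 3, 6 and 10 non-responders. It shrinks as the smaller class grows but was present in every setting examined. These sizes rest on assumed class sizes and on no true association; the optimism with a real association was not computed.

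One-class resamples are minor. They matter at about 4 or fewer non-responders and are negligible by 8 to 10.

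Two stronger readings are not supported. One is that the analysis will fail or that noise will probably produce a convincing cut-off: the documents do not establish that non-responders will be few, and even in the 3-of-30 case the average noise result is a sensitivity of only 0.54. The other is that the c-statistic is inflated: on average it is not.

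**What to change.** 1. Lead with the c-statistic, its direction fixed in advance, and with the continuous lesion-size analysis. Name the regression method and the temperature measure (difference at a stated time, or change from baseline) before the data are inspected.
2. Present the Youden cut-off, and the cut-offs at maximal sensitivity and specificity, as descriptive only.
3. Re-select the Youden cut-off in every resample, use this to estimate the optimism, and report corrected sensitivity and specificity. State how many resamples held one class and how they were handled.
4. Use exact intervals when a proportion is 0 or 100%. For 3 of 3, the exact 95% interval starts at 0.025^(1/3) = 29%, where the bootstrap with a fixed cut-off returns 100% to 100%. Exact intervals do not correct for selection.
5. State the expected number followed and expected non-responders, and a minimum size of the smaller class below which no cut-off is reported. Ten would be reasonable, but that value is a judgement.
6. Do not rely on stratified resampling as the remedy: it removes one-class resamples but neither the optimism nor the under-coverage.

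This needs SAP wording and some code, and no extra patients or measurements. The price is less favourable sensitivity and specificity, and possibly no early-response cut-off at all.
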